8.3 Definition of Intracranial Hemorrhage (ICH)

ICH is any bleeding inside the cranial vault. Intracranial is further subdivided into **intracerebral hemorrhage** (bleeding into the parenchyma of brain), **intraventricular hemorrhage** (bleeding into the ventricular system), **subarachnoid hemorrhage** (bleeding into the subarachnoid space), **subdural hematoma** (bleeding into the subdural space), and **epidural hematoma** (bleeding into the epidural space). Any intracranial hemorrhage diagnosis and typing must be confirmed by neuroimaging. Intracranial hemorrhage is further classified as symptomatic or asymptomatic and by the Pessin criteria used in the ECASS and CASES studies (PH-2, PH-1, HI-2, HI-1) [124].

Treatment-related symptomatic ICH refers to the occurrence of intracranial hemorrhage within 24 ± 6 hours of randomization, proven by neuroimaging (MRI or CT), and associated with a deterioration in neurological status. In the investigator's opinion, the hemorrhage must be thought to be the primary cause of the subject's deterioration. For example, a subject with a malignant MCA infarct and HI-2 (confluent petechial hemorrhage) would be deemed to have deteriorated from the malignant edema, rather than the HI-2 hemorrhage, and therefore, the hemorrhage would be classified as asymptomatic. It is expected that symptomatic ICH related to thrombolysis primarily consists of parenchymal hematoma hemorrhagic infarction types 1 and 2 (H1 or H2) OR subarachnoid hemorrhage OR intraventricular hemorrhage. In addition, any subject with a parenchymal hematoma types 1 or 2 (PH1 or PH2) on the 24 ± 6 hour CT scan and an increase in the NIHSS score (measured at 24 ± 6 hours) over the baseline of 4 or more points is considered to have symptomatic ICH even if the investigator does not judge the two events to be related. Any hemorrhage, however, that an investigator deems to be related is treated as symptomatic.

Asymptomatic intracranial hemorrhage refers to the occurrence of intracranial hemorrhage within $24 (\pm 6)$ hours of randomization that is not associated with worsening in the subject's neurological status.

Systemic hemorrhage. Hemorrhage other than intracranial hemorrhage. Includes gastrointestinal hemorrhage, retroperitoneal hemorrhage, epistaxis, and other bleeding. Does not include minor bleeding from the intravenous injection sites, abrasions, decubitus ulcers, etc.

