4.3.2 Screening/Baseline Evaluations

Clinical Examination: All potential subjects undergo a stroke neurological history and examination and a brief general history and examination focusing on the cardiorespiratory system. Prior medication use is documented. The time of stroke onset is determined by the stroke response team. A standardized history ensures that the subject fulfills inclusion and exclusion criteria and establishes a baseline stroke risk factor profile. Subjects undergo a standardized cardiac examination. This includes, but is not limited to, assessment of blood pressure, pulse, bedside estimation of the jugular venous pulse (JVP), auscultation of the heart for the presence of a third heart sound (S3), evaluation of a standard 12-lead EKG tracing, and evaluation of a chest X-ray, if one is done. The baseline NIHSS score is considered to be the one measured immediately prior to the start of IV thrombolysis with tPA in subjects in whom this therapy is used; and immediately before randomization in all other subjects. This is the assessment that is entered into WebDCU™ for the Baseline visit.

As a part of the initial clinical examination, all patients are assessed for potential eligibility for participation in the study. A Screening Log is maintained at each site. The Screening Log includes all patients who meet the following three requirements whether or not they ultimately participate in the study. The three criteria are: 1) 18-83 years of age; 2) clinical evidence of ischemic stroke; and, 3) were actively screened by the clinical site's ALIAS stroke team. Maintaining a Screening Log at each site helps to reduce any perception of selection bias.

Imaging: Subjects undergo a baseline neuroimaging procedure (CT or MRI) to rule out intracranial hemorrhage. The baseline CT scan should be performed using a standard stroke algorithm. A MRA and PWI are not a prerequisite of the ALIAS Trial. Save for the presence of hemorrhage, there are no exclusion criteria for the ALIAS Trial based upon the baseline CT or MRI appearance. The study is based upon the clinical diagnosis of acute ischemic stroke. Subjects who are treated with thrombolytic therapies should be treated according the local standard of care, which may require attention to the degree of ischemia shown on the baseline imaging. Baseline and 24-hour CT/MRI scans are evaluated both locally by the investigator at the time of assessment, and centrally at the University of Calgary at a later time.

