6.2.2 Evaluations During Hospitalization Following ALB/Placebo Administration

Vital signs are monitored at a minimum of four times daily (q6h) through Day 7 or Discharge, whichever occurs first. Serum chemistry is collected at 24 (\pm 6 hours) and 48 hours (\pm 6 hours). All subjects must have a serum troponin drawn as part of the 24-hour (more frequently if clinically indicated) and 48-hour collections. Fluid balance (IV intake, output) data will be collected at 24 hours (\pm 6 hours) and 48 hours (\pm 6 hours). All subjects undergo a follow-up CT scan or brain MRI (including a minimum of diffusion-weighted imaging [DWI], gradient-echo [GRE], FLAIR, and intracranial MR angiography [MRA]) at 24 hours (\pm 6 hours) from the time of randomization. All subjects also undergo a clinical assessment of neurological and cardiological status at 24 hours (\pm 6 hours), 48 hours (\pm 6 hours), and 7 days (\pm 6 hours) or discharge, whichever comes first. This includes a NIHSS evaluation and standardized cardiac assessment. An EKG should be completed once during the 24-48 hour period. Both the baseline and 24-48h EKG must be reported centrally for review.

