8.8 Monitoring of Specific Adverse Events

Incidences of the following specific adverse events are monitored by the Trial EC in a blinded manner and by the unblinded Trial personnel and the DSMB by treatment group throughout the study:

- Neurological deterioration as assessed by the investigator of an increase of 4 points or more on the NIHSS anytime within 48 (\pm 6) hours of randomization
- Neurological death from stroke during hospitalization or within 7 days (\pm 6 hours) of randomization, whichever is shorter
- Recurrent stroke within 30 (\pm 7) days of randomization
- Atrial fibrillation within 48 (\pm 6) hours of randomization
- Severe or life threatening pulmonary edema or CHF within 48 (\pm 6) hours of randomization
- Shortness of breath within 48 (\pm 6) hours of randomization
- Symptomatic ICH within 24 (\pm 6) hours of randomization
- Asymptomatic ICH as assessed by the CT scan at 24 (\pm 6) hours
- Death from any cause within 30 (\pm 7) days of randomization
- Death from any cause within 90 (\pm 14) days of randomization

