10.2.2 Secondary Outcomes

The following are outcome measures to be evaluated as supportive evidence (or lack thereof) of the ALB treatment effect: (1) mRS score at 3 months; (2) mRS score at 12 months; (3) NIHSS score at 24 hours; (4) NIHSS score at 3 months; (5) BI score at 3 months; (6) EuroQol scores at 3 months; (7) EuroQol scores at 12 months; (8) SSQOL at 3 months; (9) stroke-free status as assessed by QVSFS at 12 months; (10) ASPECTS score by CT scan at 24 (\pm 6) hours; (11) proportion of subjects who do not have symptomatic ICH within 24 (\pm 6) hours; and (12) cognition as assessed by Trailmaking A and B at 3 months. The specific treatment of each of these outcome measures is detailed in the Statistical Analysis Plan.

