As the primary analysis, all efficacy outcome measures will be analyzed under the ITT principle. Under this principle, the evaluable sample includes all subjects who are randomized, and each subject will be analyzed according to the treatment group to which they were randomly assigned and in the stratum to which they were classified at the time of randomization.

The primary analysis does not adjust for the clinical site effect due to the large number of sites (approximately 60-80). As a secondary analysis, we assess the ALB therapy effect adjusting for the effect of clinical sites. One such analysis is conducted with a generalized linear model containing treatment (ALB or placebo), thrombolysis, and baseline NIHSS as a fixed effect, clinical site as a random effect (due to the large number of sites), and treatment-by-site interaction effect as a random effect.

Other secondary analyses of the primary outcome at the end of the study include generalized linear model analysis adjusting for a variety of covariates that are deemed clinically or prognostically important (in addition to thrombolysis treatment and baseline NIHSS score). Prior to these analyses, univariate analyses of covariates are conducted to determine their inclusion in the multivariable models. Some of the variables suspected to be associated with the outcome measures are: age at baseline, African American race, serum glucose at baseline, systolic blood pressure at baseline, ASPECTS score from baseline CT scan, history of MI, and time from symptom onset to treatment. The usual verification of variable and model assumptions (e.g., normality and homoscedasticity) and goodness of fit assessments accompany each analysis.

Subgroup analyses are also planned, assuming sufficient numbers of subjects are enrolled in the subgroups. These analyses involving covariates are tested at the two-sided alpha level of 0.01 in order to control nominally for the inflation of Type I error. The details of these secondary analyses on the primary outcome measure are provided in the Statistical Analysis Plan.

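### Three 24-hour imaging measures are worded for CT only although the 24-hour scan may be MRI, so one route to symptomatic ICH depends on scanner type

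*Protocol*

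**What the plan says.** Section 6.2.2 requires a 24-hour scan of either kind: "All subjects undergo a follow-up CT scan or brain MRI". Where MRI is used, it lists minimum sequences that include diffusion-weighted and gradient-echo imaging. Section 4.3.2 sends both kinds to local and central reading: "Baseline and 24-hour CT/MRI scans are evaluated both locally by the investigator at the time of assessment, and centrally". The schedule in 6.1 likewise has combined CT/MRI rows, including one for the central reader, at baseline and 24 hours.

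Three 24-hour measures are worded more narrowly:

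- **Section 8.3, override rule.** It covers "any subject with a parenchymal hematoma types 1 or 2 (PH1 or PH2) on the" 24-hour CT scan, together with an NIHSS rise of 4 or more over baseline. Such a subject is symptomatic even when the investigator sees no link.
- **Section 8.8, monitored events.** The item reads "Asymptomatic ICH as assessed by the CT scan at 24" hours.
- **Section 10.2.2, secondary outcome 10.** It reads "ASPECTS score by CT scan at 24" hours.

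The main definition of treatment-related symptomatic ICH in 8.3 is broader. It needs a hemorrhage "proven by neuroimaging (MRI or CT") and a deterioration that the investigator attributes mainly to the bleed. The definition of asymptomatic ICH in 8.3 names no modality, and 8.3 asks only for neuroimaging to confirm hemorrhage diagnosis and type.

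**The concern.** Symptomatic ICH within 24 hours is a secondary objective (1.2), a secondary outcome (10.2.2, item 11) and an event that the DSMB follows by treatment group (8.8). The override in 8.3 is the only route to that classification that does not depend on the investigator's causal opinion. If it applies to CT alone, two subjects with the same bleed and the same neurological decline can be classified differently because of the scanner used. The scanner is chosen after randomization.

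The CT wording is hard to dismiss as shorthand, because the same paragraph of 8.3 names both modalities when it means both.

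**Working it through.** The protocol gives no figure to reproduce here, so the check is mainly a comparison of the text.

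**Step 1. Modality allowed, by section**

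| Item | Section | Modality as worded |
|---|---|---|
| 24-hour scan | 6.2.2 | CT or MRI |
| Local and central reading | 4.3.2, 6.1 | CT or MRI |
| Main symptomatic-ICH definition | 8.3 | MRI or CT |
| Hemorrhage diagnosis and typing | 8.3 | neuroimaging, not restricted |
| Asymptomatic-ICH definition | 8.3 | none named |
| PH1/PH2 plus NIHSS override | 8.3 | CT |
| Asymptomatic ICH, monitored item | 8.8 | CT |
| 24-hour ASPECTS | 10.2.2 | CT |

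**Step 2. Apply 8.3 literally to a subject with PH1 or PH2 and an NIHSS rise of 4 or more**

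| 24-hour scan | Investigator attributes the decline to the bleed | Investigator does not |
|---|---|---|
| CT | symptomatic | symptomatic (override) |
| MRI only | symptomatic (main definition) | not symptomatic |

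Only the lower right cell depends on modality.

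**Step 3. Are the data for the override present in MRI subjects?** Yes. Typing may be done on any neuroimaging (8.3), both modalities are read centrally (4.3.2), and the NIHSS is scheduled at 24 hours for everyone (6.1, 6.2.2). The limit comes from the wording, not from missing data.

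**Step 4. Asymptomatic ICH.** The 8.3 definition covers an MRI subject, while the 8.8 item as worded does not. The two sections disagree about the same event.

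**Step 5. ASPECTS.** The abbreviation list expands it as a CT score and 10.2.2 asks for it by CT. Read literally, a subject with MRI only has no value for this outcome.

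**Step 6. Size.** Let m be the share with MRI only at 24 hours. The protocol does not state m. With about 1,100 subjects, the number lacking a CT-based 24-hour ASPECTS is 1,100 × m:

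| Assumed m | Subjects |
|---|---|
| 5% | 55 |
| 10% | 110 |
| 20% | 220 |
| 30% | 330 |

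These are not misclassified bleeds. The number whose symptomatic-ICH status could change is 1,100 × m × p × (1 − a). Here p is the share of MRI-only subjects with PH1/PH2 and an NIHSS rise of 4 or more, and a is the share of those whose decline the investigator attributes to the bleed. The protocol gives neither p nor a for this group, so the product cannot be computed. It can only be smaller than the figures in the table.

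**The case against.** The strongest reply is that little can go wrong in practice. MRI subjects remain classifiable as symptomatic through the main definition, and any bleed that the investigator links to the decline counts. The Medical Safety Monitors adjudicate symptomatic ICH and could read the override sensibly. Section 8.8 is a monitoring list, so the 8.3 definition of asymptomatic ICH should govern. ASPECTS is by name a CT score, and 10.2.2 leaves the specific treatment of secondary outcomes to the SAP.

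Most of this stands, and it narrows the point to the single cell in Step 2, the mismatch between 8.3 and 8.8, and an unstated ASPECTS rule. It does not remove the point. The event definitions in 8.3 and 8.8 are not deferred to the SAP. Sites, monitors and the DSMB use them while the trial runs, and the protocol gives adjudicators no broader wording for the override.

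A reader might infer more than the text supports:

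- **That MRI subjects can never be counted as asymptomatic ICH.** The 8.3 definition names no modality, so this does not follow.
- **That the whole MRI share is misclassified.** Only the subset described in Step 6 could change status.
- **That the wording biases the arm comparison in a known direction, because volume overload steers albumin subjects to CT.** Nothing in the protocol says how modality is chosen or that it differs by arm. A numerical illustration would need an invented gap between arms. For asymptomatic ICH it would also need the zero-count premise that 8.3 contradicts.
- **That the baseline covariate, "ASPECTS score from baseline CT scan" in 10.4.1, is an equal problem.** It is only a candidate for secondary models, and 10.6 already provides for imputing missing covariates.

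**Conclusion.** The inconsistency is real and limited. As worded, the override in 8.3 makes symptomatic-ICH status depend on scanner type for subjects with MRI only, PH1/PH2, an NIHSS rise of at least 4 and no investigator attribution. The 8.8 item conflicts with the definition in 8.3, and 10.2.2 does not say what happens to 24-hour ASPECTS when only MRI exists.

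The conclusion rests on a literal reading, and on some subjects having MRI without CT at 24 hours, which 6.2.2 permits. How many is not stated. The direction of any effect on the arm comparison cannot be derived from the protocol.

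Imaging does not enter the primary outcome (10.2.1), the primary safety outcome of 30-day mortality (10.2.3), the sample size and power (10.3) or the stopping guidelines (10.7.1 and 10.7.2). The correction is worth making because it concerns a harm monitored by arm and costs very little.

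**What to change.** 1. In 8.3, let the PH1/PH2 plus NIHSS override apply to a hemorrhage seen on the 24-hour CT or MRI.
2. In 8.8, change the asymptomatic-ICH item to CT or MRI so that it agrees with the 8.3 definition.
3. In 10.2.2, state how 24-hour ASPECTS is obtained or handled when only MRI exists, or cross-refer to the SAP if it already says so. One option is the central reader's score on the diffusion-weighted sequence that 6.2.2 requires on follow-up MRI. That requirement does not extend to baseline MRI, so this option should not be carried over to the baseline covariate.
4. Record 24-hour modality and report it descriptively by arm. Do not adjust for it: it is determined after randomization, and conditioning on it could itself introduce bias.

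Items 1 and 2 cost a few words each and need no new data, since both modalities are already read centrally and the 24-hour NIHSS is already collected. Item 3 costs one sentence and, if the diffusion option is taken, extra scoring of images already sent to the central reader. Item 4 adds one descriptive table.

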The Canadian Coordinating Center, which is located in the Department of Clinical Neurosciences at the University of Calgary / Foothills Medical Centre, is responsible for the coordination and oversight of the investigators and study coordinators at the Canadian sites regarding Canadian regulatory affairs. The Canadian Coordinating Center will also function as the central review site for all neuro-imaging and EKGs.

Medical Safety Monitors (MSMs)

The MSMs are experienced stroke neurologists not affiliated with any of the institutions participating in the ALIAS Trial. The MSMs' responsibilities are to review all SAEs and determine whether they are possibly related to the study drug administration, and to adjudicate adverse outcome events (e.g., recurrent stroke, MI, symptomatic ICH). Originally, the MSMs are blinded with regard to treatment assignment of SAE cases; however, if the DSMB requests that they be unblinded, their

communications, if any, with members of the ALIAS Executive Committee will be conducted to preserve the blinded nature of the Executive Committee members.

Data and Safety Monitoring Board (DSMB)

The Data and Safety Monitoring Board (DSMB) is appointed by the NINDS Director and managed by the NINDS Clinical Trials group. Its overarching responsibility is the oversight of safety of the Trial participants. They review reports on SAEs, request additional data/information, if necessary, and must be cognizant of external new information regarding the safety of ALB treatment. Upon review of periodic data, they advise the NINDS regarding continuation of the Trial.

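### Section 8.3 sets two conflicting causal thresholds for symptomatic ICH, so a hemorrhage judged contributory but not primary can be put in either class

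*Protocol*

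**What the plan says.** Section 8.3 of the protocol contains four statements that bear on the class of a hemorrhage seen within 24 ± 6 hours of randomization.

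- **Primary-cause sentence.** The bleed must be proven by imaging and accompanied by neurological deterioration, and in the investigator's opinion the "hemorrhage must be thought to be the primary cause" of that deterioration. The worked example is a malignant MCA infarct with HI-2 petechial bleeding. The worsening is put down to edema, so "the hemorrhage would be classified as asymptomatic".
- **Objective branch.** A subject with PH1 or PH2 on the 24-hour scan and an NIHSS rise of at least 4 points over baseline "is considered to have symptomatic ICH even if the investigator does not judge the two events to be related".
- **Closing sentence.** "Any hemorrhage, however, that an investigator deems to be related is treated as symptomatic".
- **Asymptomatic ICH.** This is a hemorrhage in the same window "that is not associated with worsening in the" subject's neurological status.

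Elsewhere, the Trial Administrative Organization section gives the Medical Safety Monitors (MSMs) the task "to adjudicate adverse outcome events (e.g., recurrent stroke, MI, symptomatic ICH". Section 4.3.2 has baseline and 24-hour scans "evaluated both locally by the investigator at the time of assessment, and centrally at the University of Calgary at a later time". Section 8.5 asks the MSMs for opinions on seriousness, unexpectedness and relation to study drug; symptomatic status is not on that list. Section 10.2.2 makes freedom from symptomatic ICH secondary outcome 11. Section 8.8 lists symptomatic and asymptomatic ICH as separate events monitored by treatment group.

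**The concern.** Being the main cause of a deterioration and being related to it are different standards. The first is narrow, and the HI-2 example shows that the narrowness is intended: the patient worsens, a bleed is present, and the bleed still does not count. The second is broad, because any contribution satisfies it. Both stand in one paragraph and both are applied by the investigator, with nothing to say which governs.

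The number of sites makes this more than a drafting matter. Section 10.4.1 expects about 60 to 80 sites and the synopsis about 100. Two sites could classify identical cases differently and each could point to a sentence in Section 8.3. Because Section 8.8 tracks both classes, such a case leaves one monitored line and enters the other.

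**Working it through.** There is no figure in the protocol to reproduce. The check is to list every case that the Section 8.3 rule can meet and read off its class.

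**Inputs**, for an imaging-proven hemorrhage with deterioration inside the window:
- hemorrhage type: PH1/PH2, or other (2 levels)
- NIHSS rise over baseline: 4 or more, or less than 4 (2 levels)
- investigator's opinion: primary cause, related but not primary, or not related (3 levels)

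Combinations: 2 × 2 × 3 = 12.

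| Type and NIHSS rise | Opinion | Primary-cause sentence | Closing sentence | Result |
|---|---|---|---|---|
| PH1/PH2 and ≥4 (1 pairing) | any of 3 | overridden | overridden | symptomatic by the objective branch: 3 |
| the other 3 pairings | primary cause | symptomatic | symptomatic | agree: 3 |
| the other 3 pairings | related, not primary | not symptomatic | symptomatic | **conflict: 3** |
| the other 3 pairings | not related | not symptomatic | not symptomatic | agree: 3 |

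Total: 3 + 3 + 3 + 3 = 12. The objective branch settles 3. In the remaining 9 the investigator's opinion determines the class under Section 8.3, and in 3 of those 9 the two sentences give opposite answers.

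**Asymptomatic definition.** The last row of the table holds subjects who did worsen but whose bleed was judged unrelated. They are not symptomatic. Read literally, they are not asymptomatic either, because that class requires no associated worsening. The HI-2 example has the same difficulty: the subject has deteriorated, yet is placed in the asymptomatic class. The two passages agree only if the word associated is taken to mean attributed, and the definition does not say so.

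**Link to adjudication.** Set side by side, the administrative section assigns adjudication of symptomatic ICH to the MSMs, Section 8.3 names only the investigator, and the questions listed in Section 8.5 do not include symptomatic status. The three passages do not exclude one another, but they are not joined.

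**The case against.** The best defense is that the closing sentence is shorthand. The sentence before it speaks of whether hemorrhage and deterioration are related, so the last sentence may only be stating the converse: other hemorrhages also count when the investigator attributes the worsening to them. On that reading there is one causal judgment, loosely expressed. This is possible but strained. The sentence opens with a word that covers every hemorrhage and marks itself as a contrast to what precedes it. It also does not repeat the primary-cause condition. A site that reads it at face value would be following the text.

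A second defense is that Section 10.2.2 leaves the treatment of each secondary outcome to the SAP, which is not at hand. This stands for the question of whose classification and which scan reading enter the analysis. It does not cure the definition, because sites apply Section 8.3 when the event occurs.

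Stronger readings that a reader might infer are not supported:

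- *That the investigator's opinion always decides.* It does not. PH1/PH2 with a rise of 4 or more points overrides a negative opinion.
- *That the MSMs cannot change the class.* Nothing in Section 8.3 excludes their adjudication; the order of precedence is simply not stated.
- *That sites can recognize the arm through hemodilution and so bias the call.* The Phase I data do show a fall in hematocrit. However, the scheduled post-treatment blood work in Sections 6.1 and 6.2.2 is serum chemistry including troponin. Section 5.1 says plasma albumin should not be measured within 48 hours, and infusions are masked.

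**Conclusion.** The point holds as a contradiction within Section 8.3. Outside the objective branch, a contributory but not primary hemorrhage is symptomatic under one sentence and not under another, and the asymptomatic definition does not fit the section's own example.

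Its size in subjects cannot be calculated. Section 7.2 quotes symptomatic ICH in about 6% of subjects given IV thrombolysis, and Section 10.4.1 expects about 880 thrombolysis subjects. That gives 0.06 × 880 = 52.8, or about 53 events. A reader might multiply this by an assumed rate of disagreement between site and adjudicator to obtain a count of events that would move. The protocol gives no such rate. Disagreement between two assessors would also not measure a conflict between two sentences, and some of the 53 would be fixed by the objective branch. The same section reports one symptomatic ICH in the Phase I trial, which enrolled 82 subjects, so even the base number is uncertain.

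The expected consequence is inconsistent classification across sites, not a demonstrated bias between arms. The event is one of twelve secondary outcomes treated as supportive and tested at a two-sided 0.01. The primary safety outcome, and the safety stopping guideline in Section 10.7.2, rest on 30-day death. The correction is worth making because the rule as written yields contradictory classes and is inexpensive to repair.

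**What to change.** 1. Reconcile the primary-cause and closing sentences of Section 8.3 so that one causal threshold applies throughout. Which threshold is for the sponsor to choose.
2. Align the definition of asymptomatic ICH with that threshold, so that every imaging-proven hemorrhage in the window falls into exactly one class and the HI-2 example fits its class.
3. Keep the branch for PH1/PH2 with a rise of 4 or more points.
4. Reconcile Sections 8.3 and 8.5 with the adjudication task in the administrative section. One way is to add symptomatic status to the MSM review and to state that the adjudicated class, using the existing central imaging read, serves Section 10.2.2 item 11 and Section 8.8.

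Steps 1 to 3 are wording only. Step 4 adds one item to the MSM review. The route in Section 8.5 starts from serious events entered by the site, so hemorrhages that a site calls asymptomatic and non-serious would need a referral rule to reach the MSMs, which means some additional reviews. The monitors and the central reading are already in place.
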